**Outcome Measure**

**Primary outcome measures**

- Percentage of participants whose PLT reaches ≥

	
20*10^9/L without the need for PLT transfusion for consecutive 7 days during core study
 
Secondary outcome measures
 
 
• Percentage of participants whose PLT reaches ≥ 20*10^9/L without the need for PLT transfusion for consecutive 7 days during extended study;
 
• Percentage of participants without PLT response in the standard group but with PLT reconstruction after receiving avatrombopag;
 
• Percentage of participants with PLT ≥ 50*10^9/L without the need of PLT transfusion for consecutive 7 days during the core and extended study;
 
• The time to achieve PLT ≥ 20*10^9/L without the need of PLT transfusion for consecutive 7 days in both group;
 
• Proportion of participants achieving platelet reconstitution after 4 weeks of drug withdrawal;
 
• Volume of PLT transfusion;
 
• Hematopoietic reconstruction condition (absolute neutrophils, hemoglobin)
 
 
PLT reconstruction is defined as the status of PLT ≥ 20*10^9/L without the need of PLT transfusion for consecutive 7 days.

pSafety Measure
	
 
1. Liver and renal functions;
 
2. Occurrence and severity of transplantation-related complications;
 
3. Bleeding risk (WHO bleeding assessment scale);
 
4. Adverse events.
 

Study
	
Screening stage (Day 10~14 after Allo-HSCT)

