
Statistical Analysis
	
 
• The sponsor will utilize appropriately qualified individuals to supervise the conduct of the trial to make sure the data collection, entry and management are in accordance with good clinical practice (GCP);
 
• Corresponding database will be established and source data will be input independently;
 
• Data administrator uses Epidata software to compile data entry program and carry out following process. Two data administrators will independently enter and proofread the data in double copies to ensure the accuracy.
 
 
Sample size estimation
 
 
• 78 participants
 
 
Based on the known literature, 35% of patients in the control group and 60% of patient in the trial group were

estimated to achieve the primary endpoint. Under the condition of the number ratio of control to trial group 1:1,  $\alpha=0.05$  (bilateral) and  $1-\beta=0.9$ , the number of participants in the control group and the test group was 79 and 79 respectively, calculated by the pros and cons test method of the clinical controlled study with PASS software. Further taking into account a 20% shedding rate per group, 95 cases per group were actually needed, for a total of 190 cases

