#### **Statistical analysis method**

- PLT and other mean variation trends were processed by repeated measurement data analysis of variance; Kaplan-Meier survival analysis was used to estimate the recovery of PLT count, cumulative predicted survival rate, cumulative recurrence rate of malignant hematologic disease, cumulative mortality associated with transplantation, and cumulative incidence of GVHD, and log-rank test was performed. Independent sample nonparametric test was used to analyze the accumulative demand of PLT suspension. The statistical process and graph were all run on SPSS 13.0 software. All tests were bilateral, and  $P \leq 0.05$  was considered to be significant. The PLT recovery time, granulocyte implantation time and PLT infusion number were compared by one-way analysis of variance. OS and DFS are estimated by Kaplan-Meier method. Risk factor analysis: variables: age, sex, HLA match, CD34+ cell number, incidence of GVHD within 100 days after transplantation, CMV infection rate. Multivariate Cox regression analysis was performed on the factors with significant differences ( $P < 0.05$ ) by one-way analysis of variance.

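### Time to platelet recovery is assigned to both one-way ANOVA and Kaplan-Meier/log-rank, with neither governing and no rule for patients who do not recover

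*Combined protocol and SAP*

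**What the plan says.** All places are in the Combined protocol and SAP.

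- **Secondary outcome measures** lists "The time to achieve PLT" at or above 20×10⁹/L, transfusion-free for seven days running, in both groups. No time window is attached. Neutrophil recovery appears only as part of a general haematopoietic item, without a time definition.
- **Statistical analysis method** first states "Kaplan-Meier survival analysis was used to estimate the recovery of PLT count" and, at the end of the same list of outcomes, "cumulative mortality associated with transplantation, and cumulative incidence of GVHD, and log-rank test was performed". A few lines later: "The PLT recovery time, granulocyte implantation time and PLT infusion number were compared by one-way analysis of variance". Granulocyte implantation time is not in the Kaplan-Meier list, so ANOVA is its only method.
- **Sample size estimation** assumes "35% of patients in the control group and 60% of patient in the trial group were" expected to reach the primary endpoint, which is the same platelet criterion met during the core study.
- **Withdrawal criteria** contains a non-response rule that names avatrombopag only and sends those patients to other treatment.
- **Treatment Design** lets rhTPO non-responders receive avatrombopag after the four-week core study. **Study process** allows the same switch after visit 3.

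Nowhere do the documents give a censoring rule, a time assigned to patients who do not recover, or a restriction of the ANOVA to those who do.

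**The concern.** ANOVA needs one number per patient. Non-recovery at week 4 is the expected outcome for most controls and a large minority of avatrombopag patients, and these patients have no number. If they are left out, the two groups compared are no longer the randomised groups: recovery happens after randomisation and is what treatment is meant to change. If they are given a day, that day has to be stated, because it enters the mean directly.

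The log-rank handles these patients properly, but it stands beside the ANOVA without precedence. For a listed secondary outcome, the reported between-arm result could therefore depend on which test is chosen and on a rule not yet written.

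**Working it through.** **1. Inputs.** Recovery by the end of the core study: 35% control, 60% avatrombopag; two-sided α 0.05; power 0.90; 1:1 allocation (Sample size estimation). Core study: 28 days (Treatment Design). Headline total: 78, so 39 per arm. The same section also states 190; that conflict is a separate matter.

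**2. The plan's own figure.** Unpooled two-proportion formula: n = (1.960 + 1.282)² × (0.35×0.65 + 0.60×0.40) / 0.25² = 10.507 × 0.4675 / 0.0625 = 78.6, so 79 per group, as stated. The 35% and 60% are thus the rates the design rests on.

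**3. Patients without a time at week 4.** Control: 39 × 0.65 = 25.4. Avatrombopag: 39 × 0.40 = 15.6. Together 41 of 78, or 52.5%. This needs no assumption about timing.

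**4. What each analysis would detect.** The plan says nothing about when recoveries occur, so a shape must be assumed: exponential times reaching 35% and 60% at day 28. The hazard ratio is ln(0.40)/ln(0.65) = 2.13. Mean time among recoverers is 13.0 days (control) and 11.9 days (avatrombopag), a gap of only 1.1 days. Share of 20,000 simulated trials finding the benefit:

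| Analysis | 39 per arm | 79 per arm |
|---|---|---|
| ANOVA, recovered patients only | about 6% | 8-9% |
| ANOVA, non-recovered set to day 28 | 54% | 84% |
| Log-rank, censored at day 28 | about 62% | 90% |

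**5. Sensitivity to timing among recoverers (39 per arm).** If recovery times have the same distribution in both arms and only the share recovering differs, recovered-only ANOVA detects a benefit in about 2.5% of trials and the log-rank in about 59%. If avatrombopag recoverers are 3 days earlier (assumed SD 6), recovered-only ANOVA detects it in about 30%; if 5 days earlier, about 65%.

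**6. Sensitivity to the assigned day (39 per arm).** Setting non-recovered patients to day 28, 35, 42, 56 or 100 gives ANOVA detection of about 54, 59-60, 61-62, 62 and 62%. The mean difference moves much more. At day 28 it is 0.35×28/0.431 − 0.60×28/0.916 = 22.7 − 18.3 = 4.4 days. Each further day adds 0.65 − 0.40 = 0.25, so day 56 gives 4.4 + 28×0.25 = 11.4 days from the same patients.

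**7. Early withdrawal for non-response (hypothetical; 39 per arm, 35% recovery in both arms).** A quarter or a half of eligible avatrombopag patients leave at day 14 or 21. Nominal error in each direction is 2.5%.

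- If leavers are only patients who would never have recovered by day 28, censoring them at withdrawal falsely favours avatrombopag in about 3.6-10.4% of trials. Counting them as non-recovered is close to nominal.
- If leavers are a random sample of those unrecovered that day, censoring is close to nominal. Counting them as non-recovered falsely favours rhTPO in about 3.5-10%. Under the planned 35% and 60%, with day-14 exits, it also lowers log-rank power from about 60% to 44% (a quarter leave) or 56% to 27% (half leave).

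Neither simple rule is neutral.

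**8. Dates.** Treatment starts on day 15 after transplant. Visit 3 is day 28, which is 13 days into treatment. Four weeks of core study end on day 15 + 28 = 43. The two accounts of the rhTPO switch are about two weeks apart.

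**The case against.** The strongest reply is that the log-rank is already planned and that the plan never limits the ANOVA to recovered patients. Both statements are true. They do not say which result is reported, and they leave the ANOVA without a defined input for about half the patients.

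Four stronger readings are tempting and are not supported.

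- A reader might infer that a real benefit would nearly always be missed. That follows only if the ANOVA is run on recoverers and their timing is similar in the two arms. The plan assumes nothing about timing, and step 5 shows detection of 30% or 65% when avatrombopag recoverers are clearly earlier.
- A reader might infer that significance turns on the day assigned to non-recoverers. It moves only from about 54% to 62%. What depends on the day is the reported difference in days.
- A reader might infer that the avatrombopag-only withdrawal rule biases the log-rank towards avatrombopag, to be cured by counting leavers as non-recovered. The direction depends on who leaves, which the documents do not tell. They also leave open whether the rule acts in the core study: it cites 60 mg/d, which Treatment Design mentions only for the extended study.
- A reader might extend the concern to the primary endpoint. That is a percentage, and a patient without recovery is simply counted as such.

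For granulocytes, no non-recovery rate is given, and nothing in the eligibility criteria requires neutrophils to be unrecovered at entry. The size of the problem there is unknown.

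**Conclusion.** The concern holds for a secondary outcome. The plan names two analyses of platelet recovery time, ranks neither, and gives no rule for the 65% of controls and 40% of avatrombopag patients expected to be unrecovered at week 4. Those shares come from the plan's own rates. The shares describe week 4 only; the proportion unrecovered after the extended study is not given.

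The contrast of about 6% with about 62% at 39 per arm rests on exponential times and on restricting the ANOVA to recoverers, and should be read as an illustration. The conclusion that ANOVA is unsuitable does not rest on it: ANOVA on observed times breaks the randomised comparison, and ANOVA with an assigned day reports an effect size set by an unstated choice. The plan should be changed, but the primary result is not at risk.

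**What to change.** **Platelet recovery time.** Delete the ANOVA. Make the log-rank already planned the single governing between-arm analysis, in all FAS patients by randomised arm, over the core study. Report later recoveries descriptively, since rhTPO non-responders may then receive avatrombopag. State:

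- the time origin, and whether recovery is dated on the first or the seventh of the seven days;
- death before recovery as a competing event, and censoring at the end of the core study for patients still unrecovered;
- for patients withdrawn for non-response, continued collection of platelet counts and transfusions to the end of the core study, using their actual recovery status. Where this cannot be obtained, report the result both with censoring at withdrawal and with non-recovery assumed, since the two can err in opposite directions.

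**Before fixing the censoring day,** reconcile Treatment Design with Study process on when the rhTPO switch occurs, and Withdrawal criteria with Treatment Design on whether the non-response rule acts in the core study.

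**Granulocyte implantation time.** Use a time-to-event method here too, and say how recoveries before the day-15 start are handled.

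**Minor.** Use cumulative incidence curves for relapse, transplant-related mortality and GVHD. Kaplan-Meier overstates these, though little when events are few: with assumed rates of 10% and 5% for the event and its competitor, it reads 10.3%. The plan says "Multivariate Cox regression analysis was performed on the factors with significant differences"; GVHD within 100 days and CMV infection are among the candidates and must not be entered as if known at baseline.

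**Cost.** SAP wording, some data collection after withdrawal, confirmation that SPSS 13.0 can produce cumulative incidence curves (or naming a package that does), and a narrower window for an outcome the plan leaves open-ended.

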## **PROTOCOL SYNOPSIS**

Title	Study on avatrombopag for the promotion of platelet engraftment after allo-HSCT
---------------------	---------------------------------------------------------------------------------

Version	1.0
Population	Patients with thrombocytopenia after allogenic hematopoietic stem cell transplantation (Allo-HSCT)
Objective	To evaluate the efficacy and safety of avatrombopag in the treatment of thrombocytopenia after Allo-HSCT, and provide evidence-based instruction of avatrombopag in promoting hematopoietic function reconstruction and reducing PLT transfusion for patients with delayed PLT reconstruction after Allo-HSCT in clinical practice
Design	Single, prospective, randomized controlled trial
Subject Number	78 participants
Eligibility Criteria	
Inclusion criteria
 
Each participant must meet all of the following criteria:
 
 
1. Male or female, aged between 18-60 years;
 
2. PLT has not been reconstructed 14 days after Allo-HSCT (PLT reconstruction was defined as the status of peripheral PLT count <math>> 20 \times 10^9/L</math> for consecutive 7 days without the need for PLT transfusion);
 
3. Expected survival time <math>> 3</math> months;
 
4. ECOG performance status 0-2;
 
5. Agree to receive the treatment of avatrombopag after Allo-HSCT and must sign the informed consent form.
 
 
Exclusion criteria
 
Participant meets any of the following criteria will be excluded from this study:
 
 
1. Pregnant or lactating;
 
2. With severe and uncontrollable infection;
 
3. With graft-versus-host disease (GVHD) with steroid
 

resistance;

4. With thrombotic microangiopathy;
5. With active thromboembolism requiring anticoagulation
6. With detected disease recurrence due to chimerism by flow cytometry;
7. With chronic active hepatitis B and C virus infection;
8. With secondary or multiple transplantation, or multiple organ transplantation;
9. With severe heart disease, lung disease, diabetes and metabolic diseases;
10. HIV positive;
11. With a history of PLT dysfunction or bleeding disorders

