
process
	
 
1. Informed consent;
 
2. Subject's demographic information and basic information;
 
3. Medical history, current treatment, concomitant medication;
 
4. Vital signs, physical examination;
 
5. Transplantation mode and preprocessing scheme;
 
6. Blood test: blood routine, blood biochemical (including liver and renal functions), virus infection;
 
7. Pregnancy tests (women of childbearing age);
 
8. Eligibility criteria review.
 
 
Visit 1(Day 15 after Allo-HSCT, Initial treatment)
 
 
1. Blood test: blood routine, blood biochemical (including liver and renal functions);
 
2. Vital signs, physical examination;
 
3. Concomitant medication, including PLT transfusion;
 
4. Adverse events.
 
 
Visit 2-9 (one visit per 1~2 weeks. Visit 2, day 21±2; visit 3, day 28±2; visit 4, day 35±2; visit 5, day 42±2; visit 6, day 49±2; visit 7, day 56±2; visit 8, day 62±2; visit 9, day 70±2 after Allo-HSCT)
 
 
1. Blood test: blood routine, blood biochemical (including liver and renal functions);
 
2. Vital signs, physical examination;
 
3. Concomitant medication, including PLT transfusion;
 
4. Adverse events;
 
 
(Participants who achieved PLT reconstruction during the core and extended study period directly enter the follow up period;
 
Participants who do not respond to the standard

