
Concomitant Treatment
	
 
1. PLT transfusion is allowed according to the bleeding situation: PLT transfusion is given to participant when PLT account < 20*10^9/L, or between 21-60 *10^9/L with active bleeding;
 
2. G-CSF treatment (subcutaneous injection of G-CSF at 5 µg/kg/d from the first day after transplantation until the neutrophils count (ANC) recovered to ≥ 1*10^9/L);
 
3. Cyclosporine A, short courses of mycophenolate mofetil and methotrexate are allowed to use for the prevention of GVHD;
 
4. For medications that have been used before the trial, try to maintain the same dose during the trial;
 
5. Other TPO-RA (such as Eltrombopag and Romiplostim) should be prohibited during the study period;
 
6. Participants are allowed to take concomitant medications that are not specified as prohibited during the study period; Medications used one month prior to screening will be recorded on the case report form. All
 

	
prescription medicines, herbal medicines, nutritional supplements (including vitamins), and over-the-counter medicines should be recorded, as well as any changes in medication taken, including the dose. CYP2C9 or CYP3A4/5 medium or strong inducers may affect the exposure level of avatrombopag in vivo, and medication regimen should be comprehensively assessed by the investigator;
 
7. Observation of adverse events and concomitant medication assessment are conducted for all participants at each visit from the signing of informed consent to the end of the study;
 
8. All concomitant medications should be recorded and described in the corresponding section of the case report form (CRF).

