**Statistical analysis data set**

- **Full analysis set (FAS):** All subjects who were enrolled and had at least one dose of investigation product along with efficacy evaluation were included in FAS as per the intention-to-treat (ITT) principles. FAS contributes to the main population for efficacy evaluation in this study.
- **Per-protocol set (PPS):** PPS includes all subjects who have fulfilled the protocol-required treatment or have not seriously violated the protocol. The exact definition of serious violation will be finalized during data review, which includes but not limited to the following conditions: fails to meet the main inclusion criteria, experiences the treatment that significantly interferes with efficacy evaluation after enrollment, poor compliance, poor follow-up record that significantly beyond the time window. PPS contributes to the secondary population for efficacy evaluation in this study. However, if the analysis results of PPS are inconsistent with the FAS, detailed analysis of the inconsistent results is required.

- **Safety set (SS):** SS is defined as the data that collected from subjects receiving at least one dose of investigation product.

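### Granulocyte implantation time is compared without setting aside participants whose neutrophils recovered before the first study dose, which dilutes any real effect

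*Combined protocol and SAP*

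**What the plan says.** All references are to the combined protocol and SAP.

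- **Analysis.** Under Statistical analysis method: "The PLT recovery time, granulocyte implantation time and PLT infusion number were compared by one-way analysis of variance". No time origin, definition of granulocyte implantation, analysis set or rule for events before treatment is given.
- **Outcome.** Secondary outcome measures include "Hematopoietic reconstruction condition (absolute neutrophils, hemoglobin".
- **Timing.** Study process gives "Screening stage (Day 10~14 after Allo-HSCT" and then "Visit 1(Day 15 after Allo-HSCT, Initial treatment".
- **Eligibility.** The engraftment condition is "PLT has not been reconstructed 14 days after Allo-HSCT". No inclusion or exclusion criterion concerns neutrophils.
- **Population.** Under Statistical analysis data set: "All subjects who were enrolled and had at least one dose of investigation product along with efficacy evaluation were included in FAS". The FAS is the main efficacy population. Neither it nor the per-protocol set mentions neutrophil recovery before treatment.
- **G-CSF.** Concomitant Treatment, item 2, describes G-CSF "from the first day after transplantation until the neutrophils count (ANC) recovered to" an ANC of at least 1 × 10^9/L, with no difference by arm.

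**The concern.** The trial enrols on delayed platelet recovery, and a participant can have slow platelets while neutrophils have already recovered. Nothing in eligibility prevents this, and the first study dose comes two weeks after transplant. For such a participant the date of neutrophil recovery is fixed before either drug is given. It describes the participant at baseline, yet under the default population it enters the comparison as an outcome.

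Two things are at stake. A real effect on neutrophil recovery would be diluted and could be missed, so a null result might be read as no effect. And if the arms differ by chance in early recovery, that difference would be hard to tell from a treatment effect in the reported result.

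**Working it through.** **The plan's own figures.** None is given for granulocyte implantation time. The only computed figure is the sample size for the primary endpoint, which assumes "35% of patients in the control group and 60% of patient in the trial group were" estimated to reach it. With two-sided alpha 0.05 and power 0.90, the unpooled formula gives (1.960 + 1.282)² × (0.35 × 0.65 + 0.60 × 0.40) / 0.25² = 78.6, so 79 per arm as stated. The inflated figure is 79 × 1.2 = 94.8, so 95 per arm as stated. Neither bears on this point, except that the documents support two trial sizes: 78 / 2 = 39 per arm, and 95 per arm. Both are used below.

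**Which values precede treatment.** Screening is on days 10 to 14 and the first dose on day 15, so any recovery on or before day 14 precedes treatment. If time runs from transplant, these values are pre-treatment measurements. If it runs from first dose, they are zero or negative, and the plan has no rule for them.

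**Dilution of the mean difference.** Let f be the share recovered before the first dose and δ the true mean shift among the rest. The shift among those already recovered is zero, so the expected observed shift is f × 0 + (1 − f) × δ = (1 − f)δ. Neither f nor δ is in the documents. With δ = 4 days, an assumption:

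| f | Observed shift (days) | At risk per arm, of 39 | At risk per arm, of 95 |
|---|---|---|---|
| 30% | 4 × 0.7 = 2.8 | 27.3 | 66.5 |
| 60% | 4 × 0.4 = 1.6 | 15.6 | 38 |
| 80% | 4 × 0.2 = 0.8 | 7.8 | 19 |

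**Sensitivity.** Assume an effect that would give 80% power if everyone were still at risk, and the same SD throughout. The expected test statistic is then 1.960 + 0.842 = 2.802. Including everyone multiplies it by (1 − f). Restricting to those at risk keeps the full effect but only n(1 − f) participants, so it multiplies it by √(1 − f). Power is Φ(statistic − 1.960).

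| f | Power, everyone | Power, at risk only |
|---|---|---|
| 10% | 71% | 76% |
| 25% | 56% | 68% |
| 50% | 29% | 51% |

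The percentages are the same at 39 and 95 per arm because the effect is scaled to give 80% in each case. Under these assumptions the smaller, restricted comparison is the more sensitive one. The equal-SD assumption cannot be checked from the documents.

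**The case against.** The strongest reply is that the plan is silent rather than wrong. The analysis sentence does not say between arms, names no population and gives no time origin. No passage says that the listed neutrophil outcome will be analysed as implantation time; the repeated-measures analysis of mean trends could serve neutrophil counts equally well. That stands, and it means the documents show no deliberate decision to count early recoveries. But the measure is named for comparison in a two-arm randomised trial, the default population keeps these participants, and no rule removes them. Followed as written, the plan mixes them in.

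Three further objections also stand.

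- **Bias.** A reader might infer that early recoveries bias the result towards one arm or raise the false-positive rate. They do not: randomisation balances them in expectation, and the 5% test level already covers chance imbalance.
- **G-CSF.** A reader might infer that G-CSF given from day 1 confounds the comparison. The documents describe no difference by arm, and since it is listed under concomitant treatment they do not establish that every participant receives it. It makes early recovery plausible, no more. The argument rests on the day-15 start.
- **Time origin.** Starting the clock at first dose would not cure the problem. With everyone scheduled to start on day 15, it subtracts roughly a constant. Restricting to participants still at risk is what matters.

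Finally, f could be small, in which case little is lost.

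**Conclusion.** The point holds as a cheap improvement. The plan lets values fixed before the first dose enter a treatment comparison, and a simple restriction avoids this. The consequence is dilution by (1 − f) and a result that is hard to interpret.

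The size is unknown because the documents do not give f. The 4-day shift is also assumed, so 2.8, 1.6 and 0.8 days are illustrations, not estimates. At the highest f shown, 80%, about 8 participants per arm would be informative with 39 per arm, or 19 with 95 per arm. A reader might infer that most participants will have recovered by day 15; the documents do not support that or its opposite. Only a secondary measure is affected. The primary platelet endpoint is untouched.

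**What to change.** In the SAP:

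1. State one definition of neutrophil recovery. The ANC level of 1 × 10^9/L in Concomitant Treatment is a candidate, but there it marks the end of G-CSF and is not an engraftment definition, so the SAP must adopt it explicitly.
2. Compare neutrophil recovery between arms only among participants who had not met that definition before the first dose. Use ANC records up to and including a Visit 1 sample that is specified as pre-dose. Using all earlier records avoids misclassifying someone who recovered and then fell below the level.
3. Limit the comparison to the core study, because rhTPO non-responders may receive avatrombopag in the extended study.
4. Use the Kaplan-Meier and log-rank approach already planned for platelet recovery. One-way ANOVA has no value for participants who never recover; a time-to-event analysis keeps them.
5. Report recovery before the first dose by arm as a baseline characteristic. If few participants remain at risk, report counts only and draw no conclusion on granulocyte recovery.

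The cost is SAP wording and a smaller analysed group for one secondary measure. Blood routine is already scheduled at screening and Visit 1, so no new visit or test is needed.
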